Nonclinical data suggest that ITI-007 may have the potential to treat depression ([Snyder, 2015](#)). Antidepressant-like activity of ITI-007 was measured using the social defeat (resident-intruder) mouse model. Mice exposed to repeated social defeat conditions display a reduced amount of time in contact with unfamiliar non-aggressive mice than normal controls. Such defeat behavior is reversed by chronic (but not acute) treatment with clinically effective antidepressant drugs. In this model, 1 mg/kg ITI-007, administered once daily intraperitoneally for 28 days, reversed the defeat behavior, consistent with antidepressant efficacy.

Brain receptor target engagement was confirmed in healthy male volunteers in the ITI-007-003 positron emission tomography (PET) Phase 1 clinical study ([Davis, 2015](#)). Positron emission tomography was used to determine dopamine D₂ receptor, serotonin transporter (SERT), and serotonin 5-HT_{2A} receptor occupancy in the brain at various times following single dose oral ITI-007 administration. ITI-007 rapidly penetrated the brain, showed long-lasting and dose-related occupancy, and was generally safe and well-tolerated. Cortical 5-HT_{2A} receptors were shown to be fully occupied at 10-mg ITI-007 (>85% occupancy). A dose of 40-mg ITI-007 achieved up to 39% striatal D₂ occupancy (average of 29%) and up to 31% striatal SERT occupancy (average of 22%). Together, these data confirm a central mechanism for ITI-007 at dopaminergic and serotonergic brain targets. An additional PET study in patients with schizophrenia (ITI-007-008) demonstrated an average of approximately 40% striatal D₂ receptor occupancy at 60 mg, at plasma steady state, lower than that observed with most antipsychotic drugs. Relatively low striatal D₂ receptor occupancy likely contributes to a relatively low liability for extrapyramidal side effects and hyperprolactinemia compared with most antipsychotic drugs.

Clinical data from 3 well-controlled studies in patients with schizophrenia (ITI-007-005, ITI-007-301, and ITI-007-302) are consistent with respect to the pharmacological profile and prediction for antidepressant effects with favorable safety and tolerability. In these 3 studies, ITI-007 has been safely administered once daily for up to 42 days at doses ranging from 20 to 140 mg. Furthermore, the ITI-007 60 mg dose had a similar trajectory and magnitude of improvement in psychosis as demonstrated a reduction from baseline in the Positive and Negative Syndrome Scale (PANSS) Total Score in all 3 studies, which was statistically significant at Day 28 compared with placebo in 2 of these studies (ITI-007-005 and ITI-007-301). In addition to improving psychotic symptoms, ITI-007 also improved symptoms of depression in patients with schizophrenia and comorbid depression at baseline. Safety data from these and other trials with ITI-007 have shown that ITI-007, which has been administered to more than 1500 individuals, is well tolerated across a dose range from 1 to 140 mg and administered once daily for up to 42 days with a safety profile similar to placebo. These clinical data together with the nonclinical data and the pharmacological profile support the development of ITI-007 for the treatment of bipolar depression. Details on the profile of ITI-007 can be found in the ITI-007 Investigator's Brochure.

[figure not shown]
2 Study Objectives

[figure not shown]
2.1 Primary Efficacy Objective

The primary objective of this study is to compare the efficacy of 2 doses of ITI-007 adjunctive to treatment with lithium or valproate, administered orally once daily, to that of placebo adjunctive to treatment with lithium or valproate as measured by mean change from baseline to Day 43 in the total score on the rater-administered Montgomery-Åsberg Depression Rating Scale (MADRS) in patients with bipolar depression.

2.2 Key Secondary Efficacy Objective

The key secondary efficacy objective of this study is to compare the efficacy of 2 doses of ITI-007 adjunctive to treatment with lithium or valproate, administered orally once daily to that of placebo adjunctive to lithium or valproate as measured by mean change from baseline to Day 43 in the Clinical Global Impression Scale-Bipolar Version-Severity (CGI-BP-S)-Depression score in patients with bipolar depression.

2.4 Safety Objectives

[figure not shown]
[figure not shown]
The safety objectives of this study are to determine the safety and tolerability of 2 doses of ITI-007 adjunctive to treatment with lithium or valproate via:

- Incidence of adverse events (AEs);
- Physical examination and neurological findings;

As well as change from baseline in the following safety assessments:

- Young Mania Rating Scale (YMRS);

- Columbia Suicide Severity Rating Scale (C-SSRS);
- Abnormal Involuntary Movement Scale (AIMS);
- Barnes Akathisia Rating Scale (BARS);
- Simpson Angus Scale (SAS);
- Clinical laboratory evaluations;
- Electrocardiograms (ECGs);
- Vital sign measurements.

3 Investigational Plan

3.1 Study Design

This is a Phase 3, randomized, double-blind, parallel-group, placebo-controlled study comparing the efficacy and safety of ITI-007 versus placebo administered orally once daily in patients with bipolar depression who have had inadequate response to their depression symptoms and are currently taking one of the mood stabilizers, lithium or valproate.

The study consists of the following periods: screening period, on-treatment period, and safety follow-up period.

Screening Period (2 Weeks)

Eligible patients will be evaluated during a Screening Period up to 2 weeks in duration to ensure sufficient washout of prior and/or restricted medications. Extension of the Screening Period may be approved by the Sponsor or its representative on a case-by-case basis.

After obtaining written informed consent, diagnostic interviews and physical examinations will be conducted, vital signs and ECGs will be assessed, and blood samples for laboratory assessments will be collected. Patients considered potentially eligible for participation will be required to discontinue their current antidepressant treatment and/or other psychotropic drugs and must remain on-treatment with lithium or valproate for the duration of the study.

At Baseline (Visit 2), patients who continue to meet all eligibility criteria, including therapeutic levels of lithium or valproate, will be randomly assigned to either adjunctive ITI-007 or placebo in 1 of the 3 treatment arms for a 6-week, double-blind treatment period. Patients will be randomly assigned to one of the following groups in combination with lithium or valproate: 40-mg ITI-007, 60-mg ITI-007, or matching placebo. The random assignment will be stratified for both the first-line treatment (with lithium or valproate) and diagnosis at screening (Bipolar I or Bipolar II Disorder).

Double-blind On-treatment Period (6 Weeks)

Patients will take their first dose of study medication the evening of their baseline visit. A single dose will be taken each day in the evening for the duration of the on-treatment period.

Following randomization, patients will attend the clinic at Days 8, 15, 22, 29, 36, and 43.

The on-study treatment period will be a total of 6 weeks.

Safety Follow-up Period (2 Weeks)

A return to the clinic for a safety follow-up visit will occur at Week 8, approximately 2 weeks following the last dose of study medication. If possible, patients who withdraw prematurely will be seen for an early termination visit (within 1 week of early termination, when possible) and will be asked to return to the clinic for a safety follow-up visit 2 weeks following withdrawal.

3.1.1 Rationale of Study Design

The screening phase permits evaluation of the laboratory and ECG assessments and enables confirmation of eligibility for inclusion into the study. The screening phase will be no longer than 14 days, unless confirmed by the Medical Monitor that a longer screening phase, not to exceed 28 days, is appropriate either to ensure washout of excluded medication with long half-life (eg, fluoxetine), under the supervision of the Investigator before baseline or to ensure minimum exposure of at least 28 days to mood stabilizer (lithium or valproate) that is required to have been started by the patients of their own will, under standard of care, before the start of screening. Patients will be randomly assigned to 1 of 3 treatment groups (1:1:1) at the baseline visit and will receive treatment for up to 6 weeks. The stratified randomization will ensure that all treatment groups are balanced with regards to first-line treatment (lithium or valproate) and with regards to bipolar disorder diagnosis at study entry. In order to ensure patient safety, a mandatory 14-day follow-up visit will be performed after administration of the last dose of study medication. Any ongoing AEs at the follow-up visit must be followed until resolution, until the AE stabilizes, until it is determined to be non-clinically significant, or until the patient is lost to follow-up.

Two ITI-007 doses, as adjunctive therapy with the mood stabilizers, lithium or valproate, were selected to deliver full occupancy of the cortical 5-HT_{2A} receptors (>85% occupancy) at

both doses. Data from a human PET brain receptor occupancy study in healthy male volunteers indicates that 40-mg ITI-007 is associated with up to 39% striatal D₂ receptor occupancy (average of 29%) and up to 31% striatal SERT occupancy (average of 22%) while the 60-mg dose is projected to achieve up to 50% striatal D₂ receptor occupancy and similar or slightly less SERT occupancy. These doses have been shown to be generally safe and well tolerated and enable an exploration of the dose required to achieve efficacy in this patient population.

The doses to be administered in the present study, ITI-007 40 mg and ITI-007 60 mg, were shown to be generally well tolerated in prior studies with no evidence of a need for drug titration. Therefore, a fixed-dose design will be employed in this study.

The placebo control group is needed to establish the efficacy of a new compound.

The treatment duration of 6 weeks has been chosen because this is considered an acceptable period to demonstrate efficacy in this patient population.

4 Patient Selection and Withdrawal Criteria

4.1 Selection of Study Population

Approximately 520 patients (173 patients/arm) will be enrolled at approximately 93 study sites globally. Patients will be randomly assigned to study treatment only if they meet all of the inclusion criteria and none of the exclusion criteria.

Deviations from the inclusion and exclusion criteria are not allowed because they can potentially jeopardize the scientific integrity of the study, regulatory acceptability, or patient safety. Therefore, adherence to the criteria, as specified in the protocol, is essential.

Appropriateness of patient eligibility will be adjudicated as described in Section 3.1. Once a final decision is made, no waivers for exceptions will be provided.

4.1.1 Inclusion Criteria

Each patient must meet all of the following criteria to be enrolled in this study:

1. Is capable of understanding the written informed consent, provides signed and witnessed written informed consent, and agrees to comply with protocol requirements.
2. Is between the ages of 18 and 75 years, inclusive, at the start of screening (both male and female patients are to be included).
3. Meets the Diagnostic and Statistical Manual of Mental Disorder, 5th Edition (DSM-5) criteria for Bipolar I or Bipolar II Disorder as confirmed by the Investigator or Sponsor-approved expert site-based rater by a Structured Clinical Interview for DSM-5 Disorders – Clinical Trials Version (SCID-5-CT) (US sites only) or by the Mini International Neuropsychiatric Interview (MINI; non-US sites only) and meeting all of the following 6 criteria:
 - a. The start of the current MDE is at least 2 weeks but no more than 6 months prior to the screening visit;
 - b. Appropriate severity of illness, at least moderately ill, as measured by a rater-administered MADRS total score ≥ 20 and corresponding to CGI-BP-S Depression and Overall scores each ≥ 4 at the Screening and Baseline Visits;

- c. Sufficient history and/or independent report (such as family member or outside practitioner) verifying that the current MDE is causing clinically significant distress or impairment in social, occupational, or other important areas of functioning;
- d. A lifetime history of at least 1 bipolar manic episode or mixed episode (for Bipolar I) or hypomanic episode (for Bipolar II);
- e. A rater-administered YMRS total score of ≤ 12 at the screening and baseline visits. The presence of psychotic symptoms may result in an increased YMRS without evidence of mania/hypomania; therefore, a patient with a YMRS > 12 AND psychotic symptoms may be included pending adjudication review for diagnostic certainty of the depressive episode;
- f. A minimum of 28 days of treatment with either lithium (and 0.4 to 1.5 mEq/L blood level at screening) valproate (minimum 25 μ g/mL blood level at screening) and inadequate therapeutic response of depressive symptoms (confirmed by the treating health care provider or other reliable source). A re-test of lithium or valproate levels is not permitted; any patient who does not meet either of the two requirements must be screen failed.

- 4. Has a body mass index (BMI) of 18 to 35 kg/m^2 , inclusive;
- 5. Either must agree to use highly effective methods of birth control (defined as those, alone or in combination, that result in a failure rate less than 1% per year when used consistently and correctly) for at least 2 weeks prior to randomization (starting with signing informed consent) through to the end-of-study follow-up visit or must be of nonchildbearing potential (defined as either permanently sterilized or, if female, post-menopausal; the latter is defined as at least 1 year with no menses without an alternative medical explanation);
- 6. In the opinion of the Investigator, the patient is willing and able to comply with study requirements, study visits, and to return to the clinic for follow-up evaluations as specified by the protocol.

4.1.2 Exclusion Criteria

Patients meeting any of the following criteria will be excluded from the study:

1. The patient experiences a decrease in the rater-administered MADRS total score of $\geq 25\%$ between screening and baseline visits;
2. In the opinion of the Investigator, the patient has a significant risk for suicidal behavior during the course of his or her participation in the study or
 - a. At screening, the patient scores “yes” on Items 4 or 5 in the Suicidal Ideation section of the C-SSRS with reference to a 6-month period prior to screening; or
 - b. At screening, the patient has had 1 or more suicidal attempts with reference to a 2-year period prior to screening; or
 - c. At the baseline visit, the patient scores “yes” on Items 4 or 5 in the Suicidal Ideation section of the C-SSRS with reference to screening; or
 - d. At screening or the baseline visit, scores ≥ 4 on Item 10 (suicidal thoughts) on the rater-administered MADRS; or
 - e. Considered to be an imminent danger to himself, herself, or others.
3. The patient is pregnant or breast-feeding. Female patients of childbearing potential must have negative serum and urine pregnancy tests at screening. On Day 1, female patients of childbearing potential must have a negative urine pregnancy test prior to study treatment administration;
4. The patient has a history within 12 months of screening, based on previous psychiatric evaluation or a confirmed diagnosis upon screening based on the DSM-5 as assessed by the SCID-5-CT, (US sites only) or by the Mini International Neuropsychiatric Interview (MINI; non-US sites only), of a psychiatric diagnosis other than bipolar disorder, including:
 - a. Schizophrenia or other psychotic disorder;
 - b. Anxiety disorders such as panic disorder, general anxiety disorder, or post-traumatic stress disorder as a primary diagnosis (however, anxiety symptoms may be allowed, if secondary to bipolar disorder, provided these symptoms do not require current treatment);
 - c. Eating disorder;

- d. Primary diagnosis of obsessive-compulsive disorder;
- e. Moderate or severe substance use disorder (including for cannabis, excluding for nicotine);
- f. Any other psychiatric condition (other than bipolar disorder) that has been the main focus of treatment within 12 months of screening;

5. Patients who have experienced hallucinations, delusions, or any other psychotic symptomatology in the current depressive episode may be allowed as long as these symptoms are not attributable to a primary DSM-5 diagnosis other than bipolar disorder as described in Exclusion Criterion 4. The presence of these symptoms should be reviewed with the Medical Monitor and adjudication team on a case-by-case basis prior to inclusion;

6. The patient has been hospitalized for mania associated with Bipolar I disorder within 30 days of screening;
Note: This criterion is included to ensure that any manic phase has completely resolved before enrollment in the study.

7. The patient has received electroconvulsive therapy, vagal nerve stimulation, or repetitive trans-cranial magnetic stimulation within the last 5 years or received more than 1 course of electroconvulsive therapy during the patient's lifetime;

8. The patient is considered a rapid cycler, defined by the occurrence of at least 6 major depressive, manic, hypomanic, or mixed episodes during the previous year. These episodes must be demarcated either by a partial or full remission of at least 2 months duration or by a switch to an episode of opposite polarity. (Each MDE must have lasted at least 2 weeks, each manic or mixed episode must have lasted at least 1 week, and each hypomanic episode must have lasted at least 4 days, as validated by a reliable informant.);
Note: This criterion is included to avoid spontaneous remission during participation in the study that might confound treatment results.

9. The patient is considered treatment-resistant, defined as having a lifetime history of treatment resistance (no remission) to ≥ 2 treatments with Food and Drug Administration (FDA)-approved medications for bipolar depression (lurasidone, quetiapine, or Symbax, depending on the region) at an adequate dose (per regulatory-approved label) for an adequate duration (at least 6 weeks);

10. The patient is currently receiving formal cognitive or behavioral therapy, systematic psychotherapy, or plans to initiate such therapy during the study;
11. The patient presents with a lifetime history of epilepsy, seizure, or convulsion, or electroencephalogram with clinically significant abnormalities, delirium, dementia, amnestic, or other cognitive disorder or significant brain trauma;
12. The patient has a positive test for drugs of abuse or alcohol test at the screening or baseline visits or presents evidence of either withdrawal from or acute intoxication with cocaine, opiates, amphetamines (including methamphetamine), alcohol, barbiturates, or hallucinogens or similar compounds;

Note: Previous occasional use of alcohol or cannabis (but not synthetic marijuana/K2/Spice) or prescribed psychotropic (eg, benzodiazepine, opiate) is allowed as long as the level of use does not meet DSM-5 criteria for any moderate or severe substance use disorder within the 12 months prior to screening and the use of alcohol or cannabis is not considered to be the precipitating factor of the current depressive episode in the opinion of the Investigator and any prescribed psychotropic is accompanied by evidence of prescription; patients are required to abstain from alcohol and cannabis use during the study;

13. The patient has used one of the following agents under the specified conditions:
 - a. Lifetime exposure to ITI-007 (ie, for US sites only, participation in previous clinical study with ITI-007 as verified by DupCheck) or who has had exposure to any investigational product within 3 months of the baseline visit or participated in the past 4 years in >2 clinical studies of an investigational product with a central nervous system indication;
 - b. Any strong or moderate cytochrome P450 3A4 inhibitor or inducer within 7 days prior to the baseline visit;
 - c. Use of any short-acting anxiolytic medications within 1 week of the baseline visit or of long-acting anxiolytics within 5 half-lives of the baseline visit;
 - d. Drugs with known psychotropic properties or any non-psychotropic drugs with known or potentially significant central nervous system effects within the last 28 days or 5 half-lives before the baseline visit, whichever is less, as reviewed by the Medical Monitor, including, but not limited to:

- i. Sedative hypnotics (with the exception of zolpidem, zolpidem CR, or lorazepam as needed, no more than 3 times per week, allowed during the screening period and the first 2 weeks of the treatment period);
Note: If zolpidem, zolpidem CR, or lorazepam are not available in specific regions, another sedative hypnotic or benzodiazepine may be approved by the Medical Monitor. Medications may not be used in combination to treat insomnia;
- ii. Central opioid agonists/antagonists including tramadol (Ultram);
- iii. Anticonvulsants except valproate;
- iv. Mood stabilizers except lithium or valproate, antipsychotics, antidepressants;
- v. Methotrexate;
- vi. Any known 5-HT_{2A} receptor antagonist or inverse agonist including but not limited to mianserin, mirtazapine, nefazodone, cyproheptadine, pimavanserin, or fluvoxamine;
- vii. Immunosuppressants;
- viii. Dietary supplements and medical foods are excluded unless approved by the Medical Monitor. Daily multivitamin use is not excluded.

14. The patient has abnormal laboratory values or clinical findings at screening that are judged clinically significant and confirmed upon re-test (1 re-test prior to the Baseline Visit is allowed and results must be available prior to the Baseline Visit and must have returned to within normal range), including, but not limited to:

- a. Aspartate aminotransferase (AST) $>2.0 \times$ upper limit of normal (ULN);
- b. Alanine aminotransferase (ALT) $>2.0 \times$ ULN;
- c. Alkaline phosphatase $>2.0 \times$ ULN;
- d. Gamma-glutamyl transpeptidase $>2.0 \times$ ULN;
- e. Total bilirubin $>1.5 \times$ ULN;
- f. Serum creatinine $>1.5 \times$ ULN;
- g. Blood urea nitrogen $>1.5 \times$ ULN;

- h. Thyroid-stimulating hormone (TSH) outside of the normal limits and clinically significant, as determined by the Investigator. Free thyroxine levels may be measured if TSH level is abnormal. The patient will be excluded if the free thyroxine level is clinically significant;
- i. Any other clinically significant abnormal laboratory result at the time of the screening examination;
- j. 12-lead ECG (in a supine position at rest at the screening or baseline visit) corrected QT interval using the Fridericia formula (QTcF) > 450 ms for males or females and/or heart rate ≤ 50 beats per minute, or evidence of clinically significant bundle-branch blocks. If a patient meets the QTcF and/or heart rate exclusion criteria during the screening period, repeat ECG testing will not be permitted.

Note: If it is the opinion of the Investigator that a lower heart rate is physiological in a well-fit subject or due to stable concomitant medications, this will be reviewed and approved by the Medical Monitor on a case-by-case basis.

Note: medical conditions that are stable with medication (eg, hypertension, high cholesterol, and hyperthyroidism) are allowed as long as the condition has been stable for at least 3 months prior to screening, the medications are documented and kept stable during the study, and the condition is not thought to affect safe participation in the study in the opinion of the Investigator and confirmed by the Medical Monitor as part of the screening adjudication process.

15. The patient has clinically significant cardiovascular (including but not limited to uncontrolled angina, or history of a myocardial infarction within 3 months prior to screening, or history of a clinically significant cardiac arrhythmia including antipsychotic drug-induced corrected QT interval prolongation), endocrine (including poorly controlled diabetes defined as glycated hemoglobin A_{1c} [HbA_{1c}] >53 mmol/mol [7.0%] at screening with no re-test allowed for HbA_{1c}), hepatic, renal, pulmonary, gastrointestinal, neurological, malignancy (including any malignancy and/or chemotherapy within the 2 years prior to screening; malignancy more than 2 years prior to screening must have been local and without metastasis and/or recurrence, and if treated with chemotherapy, without nervous system complications; some malignancies, such as basal cell carcinoma, may not preclude participation and will be individually reviewed), pheochromocytoma, metabolic, psychiatric or other condition that might be detrimental to the patient if he or she participates in the study (in the opinion of the Investigator);
16. The patient has a history of human immunodeficiency virus (HIV) infection or has HIV antibodies in blood at screening;
17. The patient has a history of hepatitis B or hepatitis C infection (or is tested positive for hepatitis B surface antigen or hepatitis C antibodies) *AND* at screening has evidence of active disease defined as elevated ALT, AST, or bilirubin levels as specified in Exclusion Criterion 14;
18. The patient is an employee of the Investigator or study site, or immediate family (ie, spouse, parent, child, or sibling, whether biological or legally adopted) of such employees, the Investigator, the Sponsor, or contract research organizations (CROs) conducting the study;
19. The patient is unable to be safely discontinued from current antidepressant medication, mood stabilizers, anticholinergics, or other psychotropic medications (in the opinion of the Investigator) or unable to safely continue on current treatment with lithium or valproate;
20. The patient is judged by the Investigator to be inappropriate for the study.

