6.1.14 Columbia Suicide Severity Rating Scale

The C-SSRS is a questionnaire developed and validated by Kelly Posner and colleagues (2011) for the assessment of suicidal ideation and behavior. Several versions have been developed including the “Baseline” and “Screening” versions and a combined “Baseline/Screening” version of the scale which assesses suicidal ideation and behavior in a patient’s lifetime and during a predefined time period. This version can assess a patient’s lifetime suicidality as well as eligibility based on inclusion/exclusion criteria. A separate “Since Last Visit” version of the scale has been developed which is used to assess suicidality since the patient’s last visit. This version is meant to assess patients who have completed at least 1 initial C-SSRS assessment and should be used in every subsequent visit. The “Since Last Visit” version of the C-SSRS addresses any suicidal thoughts or behaviors the patient/participant may have had since the last time the C-SSRS was administered.

The C-SSRS will be administered by the Investigator or an expert site-based rater, as indicated in the schedule of events (Table 6-1).

At screening, a potential study participant will not be eligible if he or she reports suicidal ideation of Type 4 or 5 on the C-SSRS within 6 months prior to screening or any suicidal behavior in the last 2 years prior to screening, as indicated by any “yes” answers on the suicidal behavior section of the C-SSRS.

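### Exclusion criterion 2b covers only suicidal attempts in the 2 years before screening, while Protocol Section 6.1.14 makes any suicidal behavior in that period disqualifying

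*Protocol*

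**What the plan says.** The supplied protocol (04 September 2019) states the rule on past suicidal behavior in two forms.

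- **Criterion 2b** (synopsis and Section 4.1.2, same wording) excludes the patient if: "At screening, the patient has had 1 or more suicidal attempts with reference to a 2-year period prior to screening". It names no instrument.
- **Section 6.1.14**, which describes the C-SSRS, says that "a potential study participant will not be eligible if he or she reports suicidal ideation of Type 4 or 5 on the C-SSRS" in the 6 months before screening, "or any suicidal behavior in the last 2 years prior to screening, as indicated by any" yes among the "answers on the suicidal behavior section of the C-SSRS".

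Section 6.1.14 also says that the C-SSRS version it describes can assess "lifetime suicidality as well as eligibility based on inclusion/exclusion criteria". In the numbered list, however, only 2a and 2c name the C-SSRS, and both use its ideation section.

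Criterion 2 opens with a judgment clause: "In the opinion of the Investigator, the patient has a significant risk for suicidal behavior" while taking part. So criterion 2 itself uses both terms, behavior in its opening clause and attempts in 2b.

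On what controls entry, Section 4.1 says: "Patients will be randomly assigned to study treatment only if they meet all of the inclusion criteria and none of the exclusion criteria". Sections 3.1 and 5.1 say that "patients who continue to meet all eligibility criteria, including therapeutic levels of lithium or valproate, will be randomly assigned".

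**The concern.** A patient whose only positive C-SSRS behavior answer in the past 2 years is for something other than an attempt meets the exclusion in 6.1.14 but not the one in 2b. A site working through the numbered list could pass that patient. A site that also applies the eligibility sentence in the C-SSRS section would not.

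Two things are at stake.

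- **Safety.** Patients enter with a MADRS total of at least 20 and must stop antidepressants and other psychotropic drugs apart from lithium or valproate. One third are assigned to placebo on top of the mood stabilizer. There is no safety monitoring committee (Section 6.5) and no external DMC (Section 10.1.1). The C-SSRS is repeated at every scheduled visit (Section 6.4.2.1), but that does not replace a clear entry rule.
- **Conduct.** Section 4.1 allows no deviations from the criteria and no waivers. Section 10.2.2 treats failure to follow them as a possible significant deviation that leads to withdrawal. If such a patient is randomized, the text does not settle whether the patient was eligible.

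**Working it through.** The point involves no sample size, power or error-rate figure, so there is nothing to recompute. The check is a comparison of the two rules and a count of the other screens that might close the gap.

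**1. The two rules side by side**

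| Element | Criterion 2b | Section 6.1.14 |
|---|---|---|
| Look-back | 2 years before screening | 2 years before screening |
| Scope | Suicidal attempts, 1 or more | Any suicidal behavior |
| Instrument | None named | C-SSRS behavior section, any yes |
| Force | Exclusion criterion | Not eligible |

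The look-back agrees and the scope does not.

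**2. Is the difference confined to behavior?** Yes. The same sentence in 6.1.14 restates criterion 2a consistently: ideation 4 or 5 on the C-SSRS, 6 months. Only the behavior half departs from the numbered list, which looks more like drafting drift than two deliberate rules.

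**3. How are the rules related?** They are nested. Taking an attempt as one form of suicidal behavior, everyone excluded by 2b is also excluded by 6.1.14. The reverse does not hold: the gap is patients with a yes in the behavior section but no attempt.

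**4. Does another numbered criterion close the gap?**

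- Numbered criteria that name the C-SSRS: 2 (2a and 2c). Those that use its behavior section: 0.
- Scored screens that such a patient must also pass: 2a and 2c (C-SSRS ideation items 4 or 5) and 2d (MADRS item 10, suicidal thoughts) = 3.
- Judgment screens: the opening clause of criterion 2, 2e (imminent danger), 15 (a condition that could be detrimental to the patient) and 20 (judged inappropriate for the study) = 4.
- Total: 3 + 4 = 7.

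The three scored screens measure ideation or suicidal thoughts, not past behavior. The other four depend on the Investigator's opinion. None of the seven automatically excludes past behavior short of an attempt.

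**5. How many patients?** This cannot be derived. The documents give no rate of such behavior and do not list the C-SSRS behavior items.

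**The case against.** The strongest reply is that nested rules do not conflict. Both can be obeyed at once, and doing so gives one answer, which is to exclude. Section 6.1.14 is mandatory, Sections 3.1 and 5.1 require every eligibility criterion to be met, and Section 9.5 binds the Investigator to the whole protocol. This stands as a reading of the full text: a site that applies everything would exclude the patient. It does not cure a numbered list that carries the weaker rule and is the list Section 4.1 links to randomization.

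A second reply is that entry is not left to the site alone. Section 4.1 says eligibility is adjudicated, Section 6.1.12 refers to an adjudication process, the note under criterion 14 has the Medical Monitor confirm stable medical conditions during screening adjudication, and Section 10.2.2 implies Sponsor approval before enrollment. Such a layer exists and may catch these patients. The supplied text does not say that it tests for suicidal behavior, or which of the two rules it applies. The text of 6.1.13 (C-VISA), 6.1.17 (Eligibility Adjudication) and Table 6-1 is not in our copy, so the question stays open.

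Third, the mismatch may already be gone. The SAP (Section 2) is based on protocol version 1.6 of 23 March 2020, which we do not have. This stands, and it sets the first step of the remedy.

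Finally, the numbers are probably small, and an Investigator asked about suicidal risk would be expected to weigh recent suicidal behavior. Both are fair. They limit the weight of the point, but discretion is not the same as a fixed exclusion.

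**Conclusion.** The concern holds for the supplied protocol. It states two entry rules on suicidal behavior with the same 2-year period and different scope, and no supplied text reconciles them. The mismatch in wording is certain. Whether sites would in practice screen differently is less certain, because the admission checks and version 1.6 cannot be seen.

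The number of patients affected is unknown and probably small. No effect on the efficacy analysis or the sample size is claimed. The reasoning assumes that the C-SSRS behavior section covers more than attempts. The documents do not list its items, but the protocol's wording points that way: it speaks of any suicidal behavior and of answers in the plural. The sponsor should correct this, because it is a safety rule and the correction is cheap.

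**What to change.** 1. Check whether protocol version 1.6 already aligned the two rules.
2. If not, reword 2b in the synopsis and in Section 4.1.2 so that it excludes suicidal behavior of any kind in the 2 years before screening, defined as at least one yes in the behavior section of the C-SSRS. This also gives 2b the instrument it now lacks.
3. Send sites a short memo stating the aligned rule.

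The cost is a one-sentence change in two places, the memo, and possibly a few more screen failures. The rewording removes only patients whom Section 6.1.14 already calls ineligible, so the intended population does not change.

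Separately, and only as a clerical correction, the pointer in Section 6.4.2.1 for details of the C-SSRS should read 6.1.14 instead of 6.1.13.
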